4.2.3 Rationale for Endpoints

4.2.3.1 Efficacy Endpoints

The primary endpoint for this study is ORR, with the hypothesis that the ORR will be approximately 20% (and >5%) in patients with uveal melanoma. This ORR was chosen in that currently no effective therapies are approved for uveal melanoma and therefore an ORR in the 20% range would be highly desirable clinically. In addition, for the immune therapies, including anti-PD-1, patients who experience objective responses often have durable benefit and superior PFS and OS. Particularly for a phase II trial, therefore, ORR is an appropriate primary endpoint.

PFS and OS will also be assessed as secondary endpoints. These metrics are clearly clinically relevant although the study is not powered to assess these endpoints.

4.2.3.2 Biomarker Research

To assess whether common genetic and protein expression characteristics in uveal melanoma correlate with ORR, we will assess *GNAQ/GNA11* mutation status on each patient per institutional protocol. We will furthermore evaluate PD-L1 expression status on archival or fresh tissue from all patients and correlate with ORR.

This study will also investigate other molecular characteristics of uveal melanoma when treated with pembrolizumab. Analysis will focus on tumor and blood markers prior to therapy and early-on-treatment (at the time of the second dose).

Strongly encouraged tumor biopsies may also be performed to allow for assessment of the pharmacodynamics effects of pembrolizumab treatment. Such biopsies may be performed within 21 days of the start of treatment, and on Cycle 2 Day 1 (+/- 3 days). Assessment of these samples will include, but are not limited to, changes in lymphocyte profile in the tumor and blood.

Blood samples (2X 10 ml) will be collected as indicated in the Time and Events Table (see Section 7.1). Blood will be processed to isolate both PBMCs and serum for future biomarker analyses at the conclusion of the study, as to be determined by the investigators based on the

Protocol date: August 30, 2016

Confidential

state of knowledge at that time, and available molecular analysis platforms. Possible analyses include, but are not limited to, immune cell populations, circulating free DNA (cfDNA), circulating miRNA, and proteins/cytokines.

5.0 METHODOLOGY

5.1 Entry Criteria

5.1.1 Diagnosis/Condition for Entry into the Trial

Histologic confirmation of advanced (metastatic or unresectable) uveal melanoma. If uveal melanoma has been diagnosed clinically and/or by gene expression profiling, patients may be included following discussion with the principal investigator.

5.1.2 Enrollment Procedures

All patients MUST be registered with the [REDACTED] prior to the start of protocol treatment. Each participating site must also be registered with their own institution according to their institutional guidelines prior to start of protocol treatment. Prior to the first patient registration, a copy of IRB approval at the respective sites will be requested and on file at the VICC Coordinating Center.

[REDACTED]

- Copy of the patient's signed and dated Informed Consent
- Eligibility Checklist

5.1.3 Subject Inclusion Criteria

In order to be eligible for participation in this trial, the subject must:

1. Be willing and able to provide written informed consent/assent for the trial.
2. Be \geq 18 years of age on day of signing informed consent.
3. Have measurable disease based on RECIST 1.1.
4. Histologic confirmation of advanced (metastatic or unresectable) uveal melanoma. If uveal melanoma has been diagnosed clinically and/or by gene expression profiling, patients may be included following discussion with the principal investigator.
5. Have provided tissue from an archival tissue sample or newly obtained core or excisional biopsy of a tumor lesion.

Protocol date: August 30, 2016

Confidential

6. Have a performance status of 0 or 1 on the ECOG Performance Scale.
7. Demonstrate adequate organ function as defined in Table 1, all screening labs should be performed within 10 days of treatment initiation.

Table 1 Adequate Organ Function Laboratory Values

System	Laboratory Value
Hematological	
Absolute neutrophil count (ANC)	$\geq 1,500 / \text{mcL}$
Platelets	$\geq 100,000 / \text{mcL}$
Hemoglobin	$\geq 9 \text{ g/dL}$ or $\geq 5.6 \text{ mmol/L}$
Renal	
Serum creatinine OR Measured or calculated ^a creatinine clearance (GFR can also be used in place of creatinine or CrCl)	$\leq 1.5 \times \text{upper limit of normal (ULN)}$ OR $\geq 60 \text{ mL/min}$ for subject with creatinine levels $> 1.5 \times$ institutional ULN
Hepatic	
Serum total bilirubin	$\leq 1.5 \times \text{ULN}$ OR Direct bilirubin $\leq \text{ULN}$ for subjects with total bilirubin levels $> 1.5 \text{ ULN}$
AST (SGOT) and ALT (SGPT)	$\leq 2.5 \times \text{ULN}$ OR $\leq 5 \times \text{ULN}$ for subjects with liver metastases
Coagulation	
International Normalized Ratio (INR) or Prothrombin Time (PT)	$\leq 1.5 \times \text{ULN}$ unless subject is receiving anticoagulant therapy as long as PT or PTT is within therapeutic range of intended use of anticoagulants
Activated Partial Thromboplastin Time (aPTT)	$\leq 1.5 \times \text{ULN}$ unless subject is receiving anticoagulant therapy as long as PT or PTT is within therapeutic range of intended use of anticoagulants
^a Creatinine clearance should be calculated per institutional standard.	

8. Female subject of childbearing potential should have a negative urine or serum pregnancy within 72 hours prior to receiving the first dose of study medication. If the urine test is positive or cannot be confirmed as negative, a serum pregnancy test will be required.
9. Female subjects of childbearing potential should be willing to use 2 methods of birth control or be surgically sterile, or abstain from heterosexual activity for the course of the study through 120 days after the last dose of study medication (Reference Section 5.7.2). Subjects of childbearing potential are those who have not been surgically sterilized or have not been free from menses for > 1 year.
10. Male subjects should agree to use an adequate method of contraception starting with the first dose of study therapy through 120 days after the last dose of study therapy.

5.1.4 Subject Exclusion Criteria

The subject must be excluded from participating in the trial if the subject:

1. Is currently participating in or has participated in a study of an investigational agent or using an investigational device within 4 weeks of the first dose of treatment.
2. Has a diagnosis of immunodeficiency or is receiving systemic steroid therapy or any other form of immunosuppressive therapy within 7 days prior to the first dose of trial treatment.
3. Has had a prior monoclonal antibody within 4 weeks prior to study Day 1 or who has not recovered (i.e., \leq Grade 1 or at baseline) from adverse events due to agents administered more than 4 weeks earlier.
4. Has had prior chemotherapy, targeted small molecule therapy, or radiation therapy within 2 weeks prior to study Day 1 or who has not recovered (i.e., \leq Grade 1 or at baseline) from adverse events due to a previously administered agent.
 - Note: Subjects with \leq Grade 2 neuropathy are an exception to this criterion and may qualify for the study.
 - Note: If subject received major surgery, they must have recovered adequately from the toxicity and/or complications from the intervention prior to starting therapy.
5. Has a known additional malignancy that is progressing or requires active treatment. Exceptions include basal cell carcinoma of the skin, squamous cell carcinoma of the skin, or *in situ* cervical cancer that has undergone potentially curative therapy.
6. Has known active central nervous system (CNS) metastases and/or carcinomatous meningitis. Subjects with previously treated brain metastases may participate provided they are stable (without evidence of progression by imaging for at least four weeks prior to the first dose of trial treatment), have no evidence of new or enlarging brain metastases, and are not using steroids for at least 7 days prior to trial treatment.
7. Has an active autoimmune disease requiring systemic treatment within the past 3 months or a documented history of clinically severe autoimmune disease, or a syndrome that requires systemic steroids or immunosuppressive agents. Subjects with vitiligo or resolved childhood asthma/atopy would be an exception to this rule. Subjects that require intermittent use of bronchodilators or local steroid injections would not be excluded from the study. Subjects with hypothyroidism stable on hormone replacement or Sjorgen's syndrome will not be excluded from the study.
8. Has evidence of interstitial lung disease or active, non-infectious pneumonitis.

9. Has an active infection requiring systemic therapy.
10. Has a history or current evidence of any condition, therapy, or laboratory abnormality that might confound the results of the trial, interfere with the subject's participation for the full duration of the trial, or is not in the best interest of the subject to participate, in the opinion of the treating investigator.
11. Has known psychiatric or substance abuse disorders that would interfere with cooperation with the requirements of the trial.
12. Is pregnant or breastfeeding, or expecting to conceive or father children within the projected duration of the trial, starting with the pre-screening or screening visit through 120 days after the last dose of trial treatment.
13. Has received prior therapy with an anti-PD-1, anti-PD-L1, anti-PD-L2, or anti-CD137. Patients who received anti-CTLA4 (ipilimumab, tremelimumab) will NOT be excluded and are eligible for inclusion.
14. Has a known history of Human Immunodeficiency Virus (HIV) (HIV 1/2 antibodies).
15. Has known active Hepatitis B (e.g., HBsAg reactive) or Hepatitis C (e.g., HCV RNA [qualitative] is detected).
16. Has received a live vaccine within 30 days prior to the first dose of trial treatment.

5.2 Trial Treatments

The treatment to be used in this trial is outlined below in Table 2.

Table 2 Trial Treatment

Drug	Dose/Potency	Dose Frequency	Route of Administration	Regimen/Treatment Period	Use
MK-3475	200mg	Q3 weeks	IV infusion	2 years	Experimental

The MK-3475 dosing interval may be increased due to toxicity as described in Section 5.2.1.2.

5.2.1 Dose Selection/Modification

5.2.1.1 Dose Selection

The rationale for selection of doses to be used in this trial is provided in Section 4.0 – Background and Rationale.

The dose amount will be 200mg given intravenously every 3 weeks.

5.2.1.2 Dose Modification

Pembrolizumab will be withheld for drug-related Grade 4 hematologic toxicities, non-hematological toxicity \geq Grade 3 including laboratory abnormalities, and severe or life-threatening AEs as per Table 3 below.

Table 3: Dose modification guidelines for drug-related adverse events.

Toxicity	Grade	Hold Treatment (Y/N)	Timing for restarting treatment	Dose/Schedule for restarting treatment	Discontinue Subject (after consultation with Sponsor)
Hematological Toxicity	1, 2, 3	No	N/A	N/A	N/A
	4	Yes	Toxicity resolves to Grade 0-1 or baseline	May increase the dosing interval by 1 week	Toxicity does not resolve within 12 weeks of last infusion Permanent discontinuation should be considered for any severe or life-threatening event
Non-hematological toxicity Note: Exception to be treated similar to grade 1 toxicity 
• Grade 2 alopecia• Grade 2 fatigue For additional information regarding Adverse Events with a potential Immuno-Etiology reference Section 5.6.1.1.	1	No	N/A	N/A	N/A
	2	Consider withholding for persistent symptoms	Toxicity resolves to Grade 0-1 or baseline	Clinical AE resolves within 4 weeks: Same dose and schedule (reference Section 5.6.1.2 for recommendations regarding pneumonitis) Clinical AE does not resolve within 4 weeks: May increase the dosing interval by 1 week for each occurrence	Toxicity does not resolve within 12 weeks of last infusion

Toxicity	Grade	Hold Treatment (Y/N)	Timing for restarting treatment	Dose/Schedule for restarting treatment	Discontinue Subject (after consultation with Sponsor)
	3, 4	Yes	Toxicity resolves to Grade 0-1 or baseline	May increase the dosing interval by 1 week for each occurrence	Toxicity does not resolve within 12 weeks of last infusion Permanent discontinuation should be considered for any severe or life-threatening event

In case toxicity does not resolve to Grade 0-1 within 12 weeks after last infusion, trial treatment should be discontinued after consultation with the Sponsor. With investigator and Sponsor agreement, subjects with a laboratory adverse event still at Grade 2 after 12 weeks may continue treatment in the trial only if asymptomatic and controlled. For information on the management of adverse events, see Section 5.6.1.

Subjects who experience a recurrence of the same severe or life-threatening event at the same grade or greater with re-challenge of pembrolizumab should be discontinued from trial treatment.

5.2.2 Timing of Dose Administration

Trial treatment should be administered on Day 1 of each cycle after all procedures/assessments have been completed as detailed on the Trial Flow Chart (Section 6.0). Trial treatment may be administered up to 3 days before or after the scheduled Day 1 of each cycle due to administrative reasons.

All trial treatments will be administered on an outpatient basis.

Pembrolizumab will be administered as a 30 minute IV infusion (treatment cycle intervals may be increased due to toxicity as described in Section 5.2.1.2). Sites should make every effort to target infusion timing to be as close to 30 minutes as possible. However, given the variability of infusion pumps from site to site, a window of -5 minutes and +10 minutes is permitted (i.e., infusion time is 30 minutes: -5 min/+10 min).

5.2.3 Duration of Therapy

Pembrolizumab will be administered every 3 weeks until one of the following occurs:

- Confirmed radiographic disease progression

Protocol date: August 30, 2016

Confidential

- Indications for subject discontinuation from the trial as outlined in section 5.8
- Treatment for 24 months
- Confirmed complete response (CR)

In the event of a confirmed complete response (CR), it is at the discretion of the investigator to keep a patient on study treatment or to suspend study treatment based on the criteria.

- Radiographic CR as defined by RECIST criteria
- Confirmation with repeat imaging at least 4 weeks after the initial imaging

Patients will continue to be monitored with scheduled disease assessments as described in the protocol (as if the patient were continuing on study treatment), and in the event of a disease recurrence, pembrolizumab may be resumed (Second Course treatment) upon disease recurrence in these patients. Second Course treatment with pembrolizumab may be given for up to 12 additional months.

5.2.4 Trial Blinding/Masking

This is an open-label trial; therefore, the Sponsor, investigator and subject will know the treatment administered.

5.3 Randomization or Treatment Allocation

All patients will receive pembrolizumab 200mg IV q3W. There is no randomization in this study.

5.4 Stratification

No treatment stratification will be performed. Pre-planned analyses will evaluate response rate and PFS by expression of PD-L1 by immunohistochemistry (positive vs. negative) and by *GNAQ/GNA11* mutation status.

5.5 Concomitant Medications/Vaccinations (allowed & prohibited)

Medications or vaccinations specifically prohibited in the exclusion criteria are not allowed during the ongoing trial. If there is a clinical indication for one of these or other medications or vaccinations specifically prohibited during the trial, discontinuation from trial therapy or vaccination may be required. The investigator should discuss any questions regarding this with the coordinating center. The final decision on any supportive therapy or vaccination rests with the investigator and/or the subject's primary physician. However, the decision to continue the subject on trial therapy or vaccination schedule requires the mutual agreement of the Investigator, the coordinating center, and the subject.

5.5.1 Acceptable Concomitant Medications

All treatments that the investigator considers necessary for a subject's welfare may be administered at the discretion of the investigator in keeping with the community standards of medical care. All concomitant medication will be recorded on the case report form (CRF) including all prescription, over-the-counter (OTC), herbal supplements, and IV medications and fluids. If changes occur during the trial period, documentation of drug dosage, frequency, route, and date may also be included on the CRF.

All concomitant medications received within 28 days before the first dose of trial treatment and 30 days after the last dose of trial treatment should be recorded. Concomitant medications administered after 30 days after the last dose of trial treatment should be recorded for SAEs and ECIs as defined in Section 7.2.

5.5.2 Prohibited Concomitant Medications

Subjects are prohibited from receiving the following therapies during the Screening and Treatment Phase (including retreatment for post-complete response relapse) of this trial:

- Anti-cancer systemic chemotherapy or biological therapy
- Immunotherapy not specified in this protocol
- Chemotherapy not specified in this protocol
- Investigational agents other than pembrolizumab
- Radiation therapy
 - Note: Radiation therapy to a symptomatic solitary lesion or to the brain may be allowed after consultation with Sponsor.
- Live vaccines within 30 days prior to the first dose of trial treatment and while participating in the trial. Examples of live vaccines include, but are not limited to, the following: measles, mumps, rubella, chicken pox, yellow fever, rabies, BCG, and typhoid (oral) vaccine. Seasonal influenza vaccines for injection are generally killed virus vaccines and are allowed; however intranasal influenza vaccines (e.g. Flu-Mist®) are live attenuated vaccines, and are not allowed.
- Glucocorticoids for any purpose other than to modulate symptoms from an event of clinical interest of suspected immunologic etiology. The use of physiologic doses of corticosteroids may be approved after consultation with the Sponsor.

Subjects who, in the assessment by the investigator, require the use of any of the aforementioned treatments for clinical management should be removed from the trial. Subjects may receive other medications that the investigator deems to be medically necessary.

The Exclusion Criteria describes other medications which are prohibited in this trial.

Protocol date: August 30, 2016

Confidential

There are no prohibited therapies during the Post-Treatment Follow-up Phase.

5.6 Rescue Medications & Supportive Care

5.6.1 Supportive Care Guidelines

Subjects should receive appropriate supportive care measures as deemed necessary by the treating investigator including but not limited to the items outlined below:

- Diarrhea: Subjects should be carefully monitored for signs and symptoms of enterocolitis (such as diarrhea, abdominal pain, blood or mucus in stool, with or without fever) and of bowel perforation (such as peritoneal signs and ileus). In symptomatic subjects, infectious etiologies should be ruled out, and if symptoms are persistent and/or severe, endoscopic evaluation should be considered.
 - In subjects with severe enterocolitis (Grade 3), pembrolizumab will be permanently discontinued and treatment with systemic corticosteroids should be initiated at a dose of 1 to 2 mg/kg/day of prednisone or equivalent. When symptoms improve to Grade 1 or less, corticosteroid taper should be started and continued over at least 1 month.
 - In subjects with moderate enterocolitis (Grade 2), pembrolizumab should be withheld and anti-diarrheal treatment should be started. If symptoms are persistent for more than one week, systemic corticosteroids should be initiated (e.g., 0.5 mg/kg/day of prednisone or equivalent). When symptoms improve to Grade 1 or less, corticosteroid taper should be started and continued over at least 1 month. Regarding guidelines for continuing treatment with pembrolizumab see Section 5.2.1.2.
 - All subjects who experience diarrhea should be advised to drink liberal quantities of clear fluids. If sufficient oral fluid intake is not feasible, fluid and electrolytes should be substituted via IV infusion.
- Nausea/vomiting: Nausea and vomiting should be treated aggressively, and consideration should be given in subsequent cycles to the administration of prophylactic antiemetic therapy according to standard institutional practice. Subjects should be strongly encouraged to maintain liberal oral fluid intake.
- Anti-infectives: Subjects with a documented infectious complication should receive oral or IV antibiotics or other anti-infective agents as considered appropriate by the treating investigator for a given infectious condition, according to standard institutional practice.
- Immune-related adverse events: Please see Section 5.6.1.1 below and the separate guidance document in the administrative binder regarding diagnosis and management of adverse experiences of a potential immunologic etiology.

- Management of Infusion Reactions: Acute infusion reactions (which can include cytokine release syndrome, angioedema, or anaphylaxis) are different from allergic/hypersensitive reactions, although some of the manifestations are common to both AEs. Signs and symptoms usually develop during or shortly after drug infusion and generally resolve completely within 24 hours of completion of infusion. Signs/symptoms may include: Allergic reaction/hypersensitivity (including drug fever); Arthralgia (joint pain); Bronchospasm; Cough; Dizziness; Dyspnea (shortness of breath); Fatigue (asthenia, lethargy, malaise); Headache; Hypertension; Hypotension; Myalgia (muscle pain); Nausea; Pruritis/itching; Rash/desquamation; Rigors/chills; Sweating (diaphoresis); Tachycardia; Tumor pain (onset or exacerbation of tumor pain due to treatment); Urticaria (hives, welts, wheals); Vomiting.

Table 5 below shows treatment guidelines for subjects who experience an infusion reaction associated with administration of pembrolizumab.

Table 5 Infusion Reaction Treatment Guidelines

NCI CTCAE Grade	Treatment	Premedication at subsequent dosing
Grade 1 Mild reaction; infusion interruption not indicated; intervention not indicated	Increase monitoring of vital signs as medically indicated until the subject is deemed medically stable in the opinion of the investigator.	None
Grade 2 Requires infusion interruption but responds promptly to symptomatic treatment (e.g., antihistamines, NSAIDS, narcotics, IV fluids); prophylactic medications indicated for <=24 hrs	
Stop Infusion and monitor symptoms. Additional appropriate medical therapy may include but is not limited to:
 
 IV fluids Antihistamines NSAIDS Acetaminophen Narcotics 
Increase monitoring of vital signs as medically indicated until the subject is deemed medically stable in the opinion of the investigator.
 
If symptoms resolve within one hour of stopping drug infusion, the infusion may be restarted at 50% of the original infusion rate (e.g. from 100 mL/hr to 50 mL/hr). Otherwise dosing will be held until symptoms resolve and the subject should be premedicated for the next scheduled dose.
 
Subjects who develop Grade 2 toxicity despite adequate premedication should be permanently discontinued from further trial treatment administration.
	
Subject may be premedicated 1.5h (\pm 30 minutes) prior to infusion of MK-3475 with:
 
Diphenhydramine 50 mg po (or equivalent dose of antihistamine).
 
Acetaminophen 500-1000 mg po (or equivalent dose of antipyretic).

Grades 3 or 4 Grade 3: Prolonged (i.e., not rapidly responsive to symptomatic medication and/or brief	
Stop Infusion. Additional appropriate medical therapy may include but is not limited to:
 
 IV fluids 	No subsequent dosing

Protocol date: August 30, 2016

Confidential

NCI CTCAE Grade	Treatment	Premedication at subsequent dosing
interruption of infusion); recurrence of symptoms following initial improvement; hospitalization indicated for other clinical sequelae (e.g., renal impairment, pulmonary infiltrates) Grade 4: Life-threatening; pressor or ventilatory support indicated	
Antihistamines NSAIDS Acetaminophen Narcotics Oxygen Pressors Corticosteroids Epinephrine
 
Increase monitoring of vital signs as medically indicated until the subject is deemed medically stable in the opinion of the investigator. Hospitalization may be indicated. Subject is permanently discontinued from further trial treatment administration.
	

Appropriate resuscitation equipment should be available in the room and a physician readily available during the period of drug administration.
 
For Further information, please refer to the Common Terminology Criteria for Adverse Events v4.0 (CTCAE) at http://ctep.cancer.gov
		

5.6.1.1 Supportive Care Guidelines for Events of Clinical Interest and Immune-related Adverse Events (irAEs)

Events of clinical interest of a potential immunologic etiology (irECIs) may be defined as an adverse event of unknown etiology, associated with drug exposure and is consistent with an immune phenomenon. irAEs may be predicted based on the nature of the pembrolizumab compound, its mechanism of action, and reported experience with immunotherapies that have a similar mechanism of action. Special attention should be paid to AEs that may be suggestive of potential irAEs. An irAE can occur shortly after the first dose or several months after the last dose of treatment.

If an irAE is suspected, efforts should be made to rule out neoplastic, infectious, metabolic, toxin or other etiologic causes prior to labeling an adverse event as an irAE.

Recommendations to managing irAEs not detailed elsewhere in the protocol are detailed in Table 6.

Table 6 General Approach to Handling irAEs

irAE	Withhold/Discontinue pembrolizumab?	Supportive Care
Grade 1	No action	Provide symptomatic treatment
Grade 2	May withhold pembrolizumab	Consider systemic corticosteroids in addition to appropriate symptomatic treatment
Grade 3 and Grade 4	Withhold pembrolizumab Discontinue if unable to reduce corticosteroid dose to <	Systemic corticosteroids are indicated in addition to appropriate symptomatic treatment. May utilize 1 to 2 mg/kg prednisone or equivalent per day.

Protocol date: August 30, 2016

Confidential

	10 mg per day prednisone equivalent within 12 weeks of toxicity	Steroid taper should be considered once symptoms improve to Grade 1 or less and tapered over at least 4 weeks.
--	---	--

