5.8 Subject Withdrawal/Discontinuation Criteria

Subjects may withdraw consent at any time for any reason or be dropped from the trial at the discretion of the investigator should any untoward effect occur. In addition, a subject may be withdrawn by the investigator or the Sponsor if enrollment into the trial is inappropriate, the trial plan is violated, or for administrative and/or other safety reasons. Specific details regarding discontinuation or withdrawal are provided in Section 7.1.4 – Other Procedures.

A subject must be discontinued from the trial for any of the following reasons:

- The subject or legal representative (such as a parent or legal guardian) withdraws consent.
- Confirmed radiographic disease progression

Note: For unconfirmed radiographic disease progression in the absence of clinical deterioration, patients may continue on study.

- Unacceptable adverse experiences as described in Section 5.2.1.2
- Intercurrent illness that prevents further administration of treatment
- Investigator's decision to withdraw the subject
- The subject has a confirmed positive serum pregnancy test
- Noncompliance with trial treatment or procedure requirements
- The subject is lost to follow-up
- Completed 24 months of treatment with pembrolizumab

Note: 24 months of study medication is calculated from the date of first dose. Subjects who stop pembrolizumab after 24 months may be eligible for up to one year of additional study treatment if they progress after stopping study treatment provided they meet the requirements detailed in Section 7.1.2.6.

- Administrative reasons

The End of Treatment and Follow-up visit procedures are listed in Section 6 (Protocol Flow Chart) and Section 7.1.5 (Visit Requirements). After the end of treatment, each subject will be followed for 30 days for adverse event monitoring (serious adverse events will be collected for 90 days after the end of treatment as described in Section 7.2.3.1). Subjects who discontinue for reasons other than progressive disease will have post-treatment follow-up for disease status until disease progression, initiating a non-study cancer treatment, withdrawing consent or becoming lost to follow-up. After documented disease progression

each subject will be followed by telephone for overall survival until death, withdrawal of consent, or the end of the study, whichever occurs first.

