7.1.6.2 Treatment Period

7.1.6.2.1 Initial Treatment Period

Treatment visits will occur every 3 weeks with symptom evaluation, physical exam, and laboratory studies as documented in Section 6.0. If grade 3-4 adverse events that meet the criteria listed in Table 3, then the treatment interval may be lengthened to every 4 weeks.

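### Section 5.6.1 makes discontinuation mandatory after grade 3 enterocolitis, but Table 3 allows a restart once the event resolves, and no readable text says which rule governs

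*Combined protocol and SAP*

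**What the plan says.** **Section 5.6.1, diarrhea bullet.** For grade 3: "In subjects with severe enterocolitis (Grade 3), pembrolizumab will be permanently discontinued". The grade 2 bullet instead withholds drug and sends the question of continuing back to Section 5.2.1.2. The grade 3 bullet has no such referral.

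**Section 5.6.1, Table 5 (infusion reactions).** For grades 3 or 4: "Subject is permanently discontinued from further trial treatment administration". A grade 2 reaction that occurs despite adequate premedication also ends trial treatment permanently.

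**Section 5.2.1.2, Table 3.** For drug-related non-hematological grade 3-4 toxicity, treatment is held and may restart at grade 0-1 or baseline, with the interval lengthened by a week if wanted. Discontinuation applies if the toxicity has not resolved within 12 weeks of the last infusion. Beyond that: "Permanent discontinuation should be considered for any severe or life-threatening event". A separate sentence calls for a stop after "recurrence of the same severe or life-threatening event at the same grade or greater with re-challenge of pembrolizumab".

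**Pointers out of Table 3.** The label cell for the non-hematological rows refers events with a possible immune cause to Section 5.6.1.1. The grade 2 row adds "reference Section 5.6.1.2 for recommendations regarding pneumonitis". Below the table: "For information on the management of adverse events, see Section 5.6.1".

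**Sections that rely on Table 3.** Section 7.1.6.2.1 says that if grade 3-4 events meet the Table 3 criteria, "then the treatment interval may be lengthened to every 4 weeks". The adverse-event item in the must-discontinue list of Section 5.8 reads "Unacceptable adverse experiences as described in Section 5.2.1.2".

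**The concern.** A mandatory safety stop should read the same wherever a site looks for it. A site that starts from the dose-modification table, or from the discontinuation list in 5.8, reaches a rule that lets it restart pembrolizumab after a resolved grade 3 enterocolitis. A site that starts from the supportive-care section reaches a rule that forbids this. Re-dosing complies with Table 3 and breaches 5.6.1.

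What is at stake is one patient's re-exposure after severe bowel toxicity, together with an avoidable protocol deviation. There is a smaller knock-on effect. Sections 7.1.2.5 and 7.1.6.2.2 bar a second course when an adverse event led to discontinuation, so the choice of rule can also settle later eligibility. That matters only for patients who also meet the minimum treatment duration and later progress.

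**Working it through.** **Step 1: apply each rule to the same case.** Take a first drug-related grade 3 enterocolitis that resolves to grade 0-1 within 12 weeks of the last infusion.

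| Source | Outcome |
|---|---|
| 5.6.1, grade 3 bullet | Permanent stop, mandatory |
| Table 3, non-hematological grade 3-4 row | Restart permitted; permanent stop to be considered |
| 5.8, adverse-event item | Refers to 5.2.1.2, hence to Table 3 |
| 7.1.6.2.1 | Repeats Table 3's longer interval; adds no rule of its own |

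The word *first* matters, because 5.2.1.2 itself ends treatment on recurrence at the same or a higher grade. The 12-week limit matters because an unresolved event leads to discontinuation under both rules. Within those limits the conflict is between a mandatory and a discretionary stop: stopping satisfies both rules, and restarting satisfies only Table 3.

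**Step 2: infusion reactions.** For grade 3-4 reactions, Table 5 requires a permanent stop, while Table 3's grade 3-4 row offers a restart. For a grade 2 reaction despite premedication, Table 5 again requires a permanent stop, while Table 3's grade 2 row only asks sites to consider withholding for persistent symptoms. Table 3 makes no exception in either row.

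**Step 3: do the cross-references settle it?** The label cell leads to 5.6.1.1, where Table 6 says withhold for grade 3-4 but confines itself to immune-related events not covered elsewhere in the protocol. Enterocolitis is covered elsewhere, in 5.6.1. The sentence below Table 3 leads to 5.6.1 directly. Both pointers favor the event-specific rule, but neither says that it overrides the table.

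**Step 4: size.** The protocol gives no rate for grade 3 enterocolitis. The nearest figure is in Section 4.1.2.2: one grade 3 diarrhea case, which resolved with corticosteroids, among 135 melanoma patients in PN001. Assume that it stands in for grade 3 enterocolitis and carries over to uveal melanoma.

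- p = 1/135 = 0.0074, exact (Clopper-Pearson) 95% CI 0.0002 to 0.0406.
- Expected grade 3 cases in 29 patients: 29 × 0.0074 = 0.21 (0.005 to 1.18).
- Chance of at least one: 1 − (1 − 0.0074)^29 = 0.19 (0.005 to 0.70).

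Only events that resolve in the window are affected. Let r be the share that does, assumed to lie between 0.5 and 1. Then the expected number is N·p·r and the chance of at least one is 1 − (1 − p·r)^N.

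| N | r | Expected | Chance of at least one |
|---|---|---|---|
| 29 | 1 | 0.21 | 0.19 |
| 29 | 0.75 | 0.16 | 0.15 |
| 29 | 0.5 | 0.11 | 0.10 |
| 10 (stop after stage I) | 1 | 0.07 | 0.07 |
| 10 (stop after stage I) | 0.5 | 0.04 | 0.04 |

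These count patients to whom the conflicting rules would apply, not patients re-challenged. The documents give no rate from which to size the infusion-reaction mismatch.

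**The case against.** The strongest reply is that the rules can be reconciled. Section 5.6.1 is the specific rule and Table 3 the general one. Table 3 points towards 5.6.1 twice, from inside the table and from below it. Only the grade 2 enterocolitis bullet hands continuation back to 5.2.1.2, which suggests that the grade 3 bullet was meant to be final. The citation in 5.8 also reaches 5.6.1, by way of 5.2.1.2. Most of this stands, and it is why the stricter rule is probably intended. It remains an inference.

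Safeguards also stand in the way of actual re-challenge. Grade 3 or higher diarrhea or colitis must be reported to the sponsor within 24 hours as an event of clinical interest (7.2.3.2). Table 10 requires the clinical monitor's advance approval for re-challenge after a serious, possibly drug-caused event, or where re-exposure adds significant risk. These make an inadvertent restart unlikely, but they do not say which rule governs. The Table 10 approval itself refers to the dose-modification guidelines.

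The colitis guidance (13.4.3.2) is redacted, and the separate guidance document is not among the papers reviewed. Either may confirm the intended rule, so it cannot be said that the full plan lacks such a statement. Confirmation there would still leave Table 3 worded the other way.

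A reader might infer that the protocol directs sites to re-challenge after grade 3 enterocolitis, or that 7.1.6.2.1 grants a separate right to restart. The documents support neither. Table 3 permits a restart and tells sites to consider stopping for good; 7.1.6.2.1 only says that the interval may be lengthened.

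**Conclusion.** The inconsistency is real in the readable text, for a first drug-related grade 3 enterocolitis that resolves to grade 0-1 or baseline within 12 weeks of the last infusion, and for the permanent stops in Table 5. The event-specific rule is probably intended but is not stated to prevail.

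For enterocolitis, about 0.1 to 0.2 patients out of 29 would be affected, with a 10% to 19% chance of at least one. This takes the point estimate from a single diarrhea case and assumes that half to all such events resolve in time. The interval around that one case is wide: at r = 1, from 0.005 to 1.18 expected patients.

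A reader might also infer a threat to the primary analysis. There is none: the response-rate endpoint, the two-stage decision rules, the error rates and the sample size do not depend on which rule is followed. This is a point of safety conduct, worth correcting because the correction is cheap. Confidence is medium, because the redacted guidance could confirm the intended rule.

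**What to change.** First check the unredacted colitis guidance (13.4.3.2) for consistency. Then:

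1. Add one note to Table 3 that applies to all its rows: *Where Section 5.6.1 or its subsections and tables (including grade 3 enterocolitis, Table 5 infusion reactions and Table 7 pneumonitis) call for permanent discontinuation, that rule overrides the restart route in this table.*
2. Have the adverse-event item in 5.8 cite 5.6.1 as well as 5.2.1.2.

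Section 7.1.6.2.1 then follows through its reference to Table 3. A general note is safer than exceptions listed in the grade 3-4 row alone. Such a list would miss the grade 2 infusion-reaction stop and would imply that unlisted stops, such as those for pneumonitis, yield to Table 3. Section 5.6.1.2 currently introduces Table 7 as a suggested plan, so the clinical team should know that the note makes it firmer.

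The grade 3 bullet does not mention grade 4 enterocolitis. Whether to name it explicitly is a separate clinical confirmation.

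The cost is a wording amendment in two places and one document check, with no new visits, procedures or patients.
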